8 PLAN**

9
10
11
12

13
14
15

16 **Official Study Title: Network Dysregulation Among Individuals with
17 Co-Morbid Tinnitus and PTSD**

18

19 **NCT number: NCT03702166**

20

21 **IRB Approval Date: 02/28/2020**

22
23
24
25
26
27
28
29

30
31
32
33
34

35
36
37
38
39

40
41
42

43

44

45

46

47

48

49

50

51

52

53

54

55

56

57

58

HUMAN SUBJECTS RESEARCH PROTOCOL

61 1. **PROTOCOL TITLE:** Network Dysregulation Among Individuals with Co-Morbid Tinnitus and PTSD

62

63 2. **ABSTRACT**

64

65 Tinnitus and posttraumatic stress disorder (PTSD) are two of the most common combat-related disorders. Although the
66 defining symptoms of tinnitus (an illusory auditory percept) and PTSD (a trauma-related disorder) are clearly different, they
67 are highly comorbid. Neurobiologically, each disorder has been characterized as functional network dysregulations, applying
68 functional co-variance (FCov) metrics to resting-state functional magnetic resonance imaging (rs-fMRI). In PTSD, network
69 abnormalities have been reported in the attention, limbic and default-mode networks. In tinnitus, the same networks have
70 been reported as abnormal, with the addition of the auditory network. Given the hypothesized shared neurobiological resting
71 state networks between tinnitus and PTSD, it is anticipated that treatment of PTSD will also help alleviate tinnitus distress.

72

73 The purpose of this study is to characterize tinnitus and PTSD symptomatically, neurobiologically, and causally, applying
74 causal modeling to psychometric and neurofunctional data. We will enroll 30 individuals with both tinnitus and PTSD.
75 Participants will be asked to complete baseline assessments of subjective tinnitus distress, PTSD, depression, and resting-
76 state fMRI at baseline. Individuals with comorbid tinnitus and PTSD who are eligible for the study will receive Cognitive
77 Processing Therapy (CPT) over a 6- to 15-week period and a mid-treatment resting-state fMRI (after Session 6 of CPT and
78 before Session 7 of CPT). CPT is a trauma-focused treatment for PTSD that guides individuals on how to recognize and
79 challenge thoughts that are erroneous and dysfunctional. One-month follow-up assessments of tinnitus-related distress,
80 PTSD, depression, and anxiety will be conducted, along with resting-state fMRI.

81

82 3. **OBJECTIVES/SPECIFIC AIMS/RESEARCH QUESTIONS**

83

84 **Objective:**

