85 The primary objective of this study is to evaluate the overlap between tinnitus-related distress and symptoms of PTSD,
86 identify functional covariance among resting-state networks among individuals with tinnitus and PTSD, and determine
87 psychometric and neurobiological changes among participants who receive Cognitive Processing Therapy (CPT for
88 PTSD).

89

90 **Aim 1:** To identify the cognitive, behavioral, and emotional symptoms that are both shared and unique to PTSD and
91 tinnitus-related distress.

92

93 **Hypothesis 1:** There will be significant overlap between tinnitus distress and PTSD symptoms, as measured by the
94 Clinician Administered PTSD Scale for DSM-5 (CAPS-5), the PTSD Checklist for DSM-5 (PCL-5), the Tinnitus Functional

97 Index (TFI), and Tinnitus Acceptance Questionnaire (TAQ). Findings will help clinicians' understanding of the distinct ways
98 in which each disorder contributes to functional impairment. Results will substantially improve clinicians' ability to
99 conceptualize patients with comorbid tinnitus and PTSD.

100 **Aim 2:** To identify the functional covariance among resting-state networks, including the limbic, attentional, auditory, and
101 default-mode networks associated with tinnitus and PTSD. Resting state fMRI techniques will be conducted among
102 individuals with comorbid PTSD and tinnitus.

103 **Hypothesis 2:** There will be similar neurological activity associated with PTSD and tinnitus as measured by resting state
104 fMRI. Down-regulation and up-regulation of neurobiological connectivity of the networks will be examined within the
105 auditory, limbic, default-mode, and attentional networks. Results will provide insight concerning the neurological
106 maintenance factors for both disorders. Study findings will be utilized to generate new and innovative therapeutic
107 approaches that target specific brain regions to alleviate tinnitus and PTSD.

108 **Aim 3:** To determine relationships psychometrically, neurobiologically (as rs-fMRI network differences), and conjointly
109 (between psychometrics and rs-fMRI). Longitudinal measures will determine both psychometric and neurobiological
110 changes among participants who complete Cognitive Processing Therapy for PTSD (CPT for PTSD).

111 **Hypothesis 3:**

- 112 ▪ Individuals with tinnitus and PTSD who received Cognitive Processing Therapy will demonstrate significant

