461 Hypothesis 2: There will be similar neurological activity associated with PTSD and tinnitus as measured by resting state
 462 fMRI. Down-regulation and up-regulation of neurobiological connectivity of the networks will be examined within the
 463 auditory, limbic, default-mode, and attentional networks. Results will provide insight concerning the neurological
 464 maintenance factors for both disorders. Study findings will be utilized to generate new and innovative therapeutic
 465 approaches that target specific brain regions to alleviate tinnitus and PTSD.
 466

467 Analysis plan: An inter-regional connectivity mapping using an extended time-series (typically 200-400 whole-
 468 brain volumes acquired over 8-15 minutes) of BOLD fMRI images acquired in an unstimulated state (Biswal et al.,
 469 1995; Xiong et al., 1999) will be utilized for Aim 2. Inter-connected regions show temporally correlated variations,
 470 allowing connectivity to be detected and quantified. Resting-state networks (RSNs) have been used to map
 471 scores of functional systems. They are now viewed as reflecting the intrinsic architecture of the brain (Smith et al.
 472 2009). Resting-state connectivity analysis of the auditory system in normal subjects demonstrated highly coherent
 473 within-system connectivity, as well as strong projections to the frontal limbic circuitry (Hunter et al., 2006).
 474 Resting-state connectivity analyses will be used to characterize tinnitus-related network abnormalities.
 475

Hypothesis 3:

- Individuals with tinnitus and PTSD who received Cognitive Processing Therapy will demonstrate significant reductions in both PTSD symptoms and tinnitus-related distress at a one-month follow-up assessment, AND
- After one month of completing CPT for individuals with both PTSD and tinnitus, a decrease in neurobiological connectivity will be demonstrated between the attention network and limbic network, demonstrating the role of cognitive control in reducing psychological distress.

Analysis plan: Post-treatment outcome data will be compared to participants' baseline measures of tinnitus-related distress and PTSD. Data will be analyzed using a general linear mixed (GLM) model with baseline scores of tinnitus-related distress used as a covariate. The analyses will demonstrate whether individuals who received CPT experienced a reduction in tinnitus-related distress and PTSD symptoms.

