An inter-regional connectivity mapping using an extended time-series (typically 200-400 whole-brain volumes acquired over 8-15 minutes) of BOLD fMRI images acquired in an unstimulated state will be utilized for Aim 3. Resting-state connectivity analyses will be used to better characterize tinnitus-related network abnormalities using Independent Components Analysis, using analysis of variance (ANOVA) comparing Baseline versus Posttreatment factors, while regressing out demographic variables. The mid-treatment scan will be used to infer causal effects of Cognitive Processing Therapy by demonstrating the temporal changes in resting-state networks.

Missing data. If missing data can be assumed to be missing at random, likelihood-based mixed model analysis will provide valid inferences using data from all cases with any outcome data. The impact of attrition on analyses will be addressed by comparing those who are available for analysis at each assessment with those who are not using appropriate data from prior assessments.

6.7 Confidentiality. All in-person therapy sessions and interview assessments will be delivered in private offices at the STRONG STAR Clinic at the UTHSCSA. Data will be stored by an assigned participant code number. Digital audio recordings of assessments and CPT sessions will be labeled with the participant's study id number and uploaded onto the secure STRONG STAR server. Encrypted email will be used to securely send recordings to research experts who are part of the research team for review of fidelity. Every member of the Research Team will be trained and monitored about how to handle and protect both medical and research records. Furthermore, the Research Team strictly controls access to study data.

6.7.1 Certificate of Confidentiality.

We are not seeking a Certificate of Confidentiality.

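### Hypothesis 2 compares PTSD-associated with tinnitus-associated activity, but every participant has both disorders and no reference is planned, so the plan can describe connectivity but not test the hypothesis

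*Combined protocol and SAP*

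**What the plan says.** **The hypothesis.** Sections 3 and 6.4.3 state it in the same words: "There will be similar neurological activity associated with PTSD and tinnitus", on resting-state fMRI. Both places add that up- and down-regulation of connectivity will be examined in the auditory, limbic, default-mode and attentional networks, and that the results will bear on what maintains both disorders.

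**The sample.** The abstract says: "We will enroll 30 individuals with both tinnitus and PTSD". Section 6.1.3 requires a PTSD diagnosis on the CAPS-5 and bothersome tinnitus, with a TFI score of at least 32. Section 5 describes one group receiving one intervention.

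**The analysis plan for Hypothesis 2 (6.4.3).** It describes inter-regional mapping of the BOLD time series and ends: "Resting-state connectivity analyses will be used to characterize tinnitus-related network abnormalities". Its one mention of a normal population, "Resting-state connectivity analysis of the auditory system in normal subjects", reports a cited study.

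**Neighbouring text.**
- The Hypothesis 3 plan aims to "better characterize tinnitus-related network abnormalities using Independent Components Analysis", with an ANOVA "comparing Baseline versus Posttreatment factors".
- Aim 3 is "To determine relationships psychometrically, neurobiologically (as rs-fMRI network differences), and conjointly", that is, between the psychometric and imaging measures. Section 6.4.3 gives no model for the conjoint part.
- The abstract mentions causal modeling of both kinds of data, and the background (section 4) repeats the conjoint aim. Neither gives a model.
- Section 4 also says the study will characterize each disorder on its own as well as in combination.

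**The concern.** Hypothesis 2 compares two quantities: the activity that goes with PTSD and the activity that goes with tinnitus. To find them similar or different, the data must let each be estimated. Here no one has only one of the disorders and no one has neither. The plan also promises to identify abnormalities without saying what normal is.

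Any connectivity pattern found at baseline would be compatible with the hypothesis and equally with its negation. The risk is that an ordinary map of connectivity in comorbid patients is reported as evidence of shared PTSD and tinnitus neurobiology, and then used, as the hypothesis text foresees, to choose brain regions for new treatments.

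**Working it through.** **The plan's own figure.** Section 6.4.1 gives 30 recruited, 18 screened out and 2 withdrawn: 30 - 18 - 2 = 10, with 18/30 = 60% and 2/30 = 6.7%. The arithmetic closes. The 10 is justified for differences between the pre-, mid- and posttreatment scans, not for Hypothesis 2. No alpha, power, effect size or SD is stated, so the power claim cannot be reproduced.

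**Step 1: disorder presence.** Inputs are the inclusion criteria (6.1.3) and the single group (section 5). Code PTSD and tinnitus as 0 or 1:

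connectivity = b0 + b1·PTSD + b2·tinnitus + b3·PTSD·tinnitus

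Every participant has PTSD = tinnitus = 1, so each row of the design matrix is (1, 1, 1, 1). Only the sum b0 + b1 + b2 + b3 can be estimated.

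| Sample | Model | Rank / parameters |
|---|---|---|
| Planned: comorbid only, n = 10, 12 or 1,000 | with interaction | 1 / 4 |
| Planned: comorbid only | additive | 1 / 3 |
| Healthy plus comorbid | additive | 2 / 3 |
| PTSD only, tinnitus only, comorbid | additive | 3 / 3 |
| All four cells | with interaction | 4 / 4 |

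A healthy group alone would define abnormality but would not separate the disorders.

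Illustration with assumed values and no interaction: a comorbid mean of 0.5 is fitted equally well by 0.1 + 0.2 + 0.2 (both disorders contribute equally), 0.1 + 0.4 + 0 (PTSD only), 0.1 + 0 + 0.4 (tinnitus only) and 0.5 + 0 + 0 (neither).

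**Step 2: abnormality and regulation.** Both need a reference value. At baseline the plan has none. The pre-treatment scan is a reference for change within a person under Hypothesis 3, not for departure from normal.

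**Step 3: disorder severity.** CAPS-5 and TFI scores vary between participants, so a matrix of intercept, CAPS-5 and TFI has rank 3 of 3. With an assumed correlation rho between the two scores, the variance inflation is 1/(1 - rho²): 1.10, 1.33 and 1.96 at rho = 0.3, 0.5 and 0.7. Severity associations are identifiable. The limit is precision, assuming a two-sided 0.05 level and 80% power:

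- Detectable r by Fisher z = tanh[(1.960 + 0.842)/√(n - 3)]: 0.785 at n = 10 and 0.732 at n = 12 (30 - 18, before withdrawals). The approximation is slightly conservative.
- Smallest significant |r| = t/√(n - 2 + t²): 0.632 at n = 10 and 0.576 at n = 12.
- 95% interval for an observed r of 0.5 = tanh[0.549 ± 1.96/√(n - 3)]: -0.19 to 0.86 at n = 10 and -0.10 to 0.83 at n = 12.
- Adjusted for the other disorder's severity at n = 10: smallest significant partial |r| is 0.666; detectable, tanh[2.802/√6] = 0.816.

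**Step 4: does other text fill the gap?** Independent Components Analysis (section 14.0) extracts networks and does not assign them to a disorder. The ANOVA in the Hypothesis 3 plan contains no clinical scores, so it cannot relate connectivity to either disorder. The mentions of causal or conjoint analysis in sections 2, 3 and 4 state an intention without a model.

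**The case against.** The strongest reply is that the protocol treats overlap dimensionally. Hypothesis 1 correlates CAPS-5 and TFI measures in these same participants (6.4.3), and activity associated with PTSD can be read as activity that varies with PTSD severity. On that reading the sample does carry information, and more participants would help.

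This stands, and it limits the point. A reader might infer that no analysis of these data could ever separate the two disorders. The documents do not support that: the rank result covers presence against absence only. A reader might also infer that, because Hypothesis 3 expects PTSD symptoms and tinnitus distress to fall together, the longitudinal data cannot separate them. That does not follow either. Falls in both means do not make individual changes collinear, and section 6.2 schedules the PCL-5 and TFI repeatedly during treatment.

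The reply does not rescue Hypothesis 2 as planned. Its analysis plan includes no clinical score, and severity associations would still not define an abnormality.

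It may also be said that the eligibility wording on seeking treatment for either or both conditions admits single-disorder participants. It does not. It concerns treatment seeking, and both conditions remain required.

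Finally, this is a small study and might fairly be exploratory. The text does not say so for Hypothesis 2.

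**Conclusion.** The concern holds for Hypothesis 2 as written. The plan can describe resting-state connectivity in people with both disorders. It cannot support or contradict a statement that PTSD and tinnitus, as disorders, have similar associated activity, and it has no baseline reference for abnormality or for up- and down-regulation.

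For disorder presence this is a complete failure of identification (rank 1 of 4) and does not depend on n. For severity it is a missing specification together with low precision at about 10 participants. The precision figures assume a two-sided 0.05 level and 80% power, neither of which the protocol states.

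The reach is limited. Aim 2's descriptive mapping and the primary outcomes in 6.4.2, which are changes over time, are unaffected. The text should be corrected because one of three stated hypotheses would otherwise yield a conclusion the data cannot bear.

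**What to change.** 1. **Section 6.4.3, Hypothesis 2 plan:** keep the connectivity mapping as the descriptive analysis for Aim 2.
2. **Sections 3 and 6.4.3, Hypothesis 2:** restate it as exploratory and descriptive, in comorbid participants only, with no conclusion that activity is specific to, or similar between, PTSD and tinnitus as disorders. Delete the up- and down-regulation sentence or limit it to within-person change from baseline. Limit the sentence on maintenance of both disorders to hypothesis generation.
3. **Section 6.4.3, Hypothesis 2 and 3 plans:** replace the references to abnormalities related to tinnitus with *resting-state network connectivity in participants with comorbid PTSD and tinnitus*.
4. **Sections 2 and 4:** limit to comorbid participants the abstract's aim of characterizing the disorders neurobiologically and causally, and the background claim to characterize each disorder on its own.

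The background sentence about functional covariance common to both disorders can stay, since it can be read as covering networks that the literature already implicates in both. Baseline severity correlations are not proposed as a repair for Aim 3, whose conjoint relationship rests on longitudinal change and needs its own model.

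**Cost:** wording in four sections, with no new participants, visits or scans. The price is that Hypothesis 2 narrows to description.

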5. RESEARCH DESIGN

The study will use a one-way experimental design, with one level of intervention: Cognitive Processing Therapy (CPT). Participants will complete initial baseline assessments to determine eligibility, as well as resting-state fMRI scans. After completing baseline assessments and fMRI scans, participants will be scheduled 1 therapy session to discuss psychosocial history, trauma, and current functioning, which will last approximately 1 hour. Afterwards, participants will be scheduled for 12 50-minute sessions of CPT, either once or twice per week, for 6 to 15 weeks. After completing Session 6 of CPT and before Session 7 of CPT, participants will be scheduled for a mid-treatment fMRI scan. After completing CPT, participants will be scheduled for a one-month follow-up assessment, as well as a one-month follow-up fMRI scan.

Figure 1. Study Design Overview.

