318 participant will be given a copy of the informed consent document (ICD) to read. The research team member obtaining
319 informed consent will then engage the potential participant in an interactive explanation of the study guided by the ICD.
320 After the subject has read the ICD, he or she will be given the opportunity to consider participation and discuss the
321 research with family and friends. The Research Team will be available to answer any questions about the research.
322 Once the potential participant has reached a decision, the advising staff member will review the risks and benefits of study
323 participation and ensure the subject has an understanding of the material discussed, and the risks and benefits of their
324 potential involvement in the study. The advising staff member will have the participant sign the consent form. A copy of
325 the signed ICD will be given to the subject.
326

327 **6.1.6. Subject Screening Procedures.**

328 Following consent, screening and baseline assessment will take place to determine participant eligibility. The entire
329 screening process will take approximately 3 hours. This will include the completion of the questionnaires and interviews
330 outlined in the table in Section 6.2 below. For individuals not meeting study inclusion criteria, the Study Staff will assist
331 coordinating appropriate care outside of the study.
332

333 **6.1.7. Compensation for participation.**

334 Participants will be compensated \$75 for each neuroimaging scan: once prior to enrolling in Cognitive Processing
335 Therapy, once at mid-treatment (after Session 6 and before Session 7), and once at the one-month follow-up after
18-524H, [name], Form BB, 02-28-20, AMD.DOCX
Page 7 of 22

336 receiving Cognitive Processing Therapy. Payment will be provided via a rechargeable MasterCard® ClinCard. The
337 MasterCard® ClinCard is a debit card issued to the study participant. Funds are loaded onto card through the ClinCard
338 website at www.clincard.com. Only authorized users will be able to access the ClinCard website to add funds with a
339 username and password. The ClinCard funds will be available to recipients within 1 business day and can be used as the
340 participant chooses. The participant will be notified that their name, address and date of birth will be shared with a third-
341 party (ClinCard) solely for the purposes of payment processing. This information will only be used for the administration

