365 beliefs, they have difficulty reconciling events that appear to be unfair or random. People also tend to blame themselves
366 for events or try to mentally “undo” the event and feel guilt, shame or anger, rather than the natural emotions that may
367 have emanated directly from the event (sadness/grief, fear, horror) (Resick, Galovski, et al., 2008). All study participants
368 will receive treatment with CPT, as it is typically conducted in the VA or another clinic, face-to-face. The patient will be
369 seen either once or twice a week in the clinic office and the therapist will follow the protocol as specified in the manual.
370 The patient will be given assignments that will be placed into a patient binder for them to keep. However, the therapist will
371 also keep a folder with a copy of the stuck point log and extra copies of worksheets in case the patient forgets to bring the
372 binder to the session.

373 374 **Training, Certification, and Supervision of CPT Therapists**

375 A detailed CPT training, certification, and supervision process has been developed to ensure that CPT is delivered
376 according to protocol and with the highest levels of quality and fidelity. The Principal Investigator ([name]) is a
377 licensed clinical psychologist with extensive training and consultation provided by one of the developers of CPT, Dr.
378 [name]. [name], Consultant on this research study, will provide consultation on an as-needed basis.

380 381 **Treatment Adherence and Competence.** The fidelity to the treatment will be closely monitored to ensure that the
382 therapy is being delivered true to the protocol. Treatment adherence and competence will be determined by independent
383 raters who are not otherwise involved in the project. The raters will be affiliated STRONG STAR investigators who have
384 served on prior CPT studies as adherence and competence raters. In order to ensure that the CPT treatment is
385 administered in accordance with the manual, all sessions in the study will be audio recorded for fidelity rating. Audio
386 recordings will be uploaded onto the secure STRONG STAR server so they can be reviewed remotely. The raters will
387 determine adherence to the CPT therapies and competence in delivering the therapies. Five percent of all audiotapes for
388 listening and determination of inter-rater reliabilities (kappas).

389 **6.2. Study Procedures.**

390

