The recruited sample size will be 30 participants. Based on work by Salinas and Szabo (2017), 10 participants will provide adequate power to detect differences in resting-state networks, from pre-, mid- and to posttreatment fMRI scans. In their

428 paper, they examined 14 baboons, pre- and posttreatment injection of valproic acid, at three different time points, with
 429 adequate power.
 430

Estimate Required Sample Size	10
Estimate Participant Screen Out	18 (~60%)
Estimate Participant Withdrawal	2 (~7%)
Total Enrollment Requirement	30

431
 432
 433
434 6.4.2 Primary (i.e., primary outcome variables) and secondary endpoints.
 435

436 Primary outcomes include changes in scores on measures of PTSD (CAPS-5 and PCL-5) and tinnitus-related distress (TFI
 437 and TAQ). The additional primary outcome is changes in functional activity within resting-state networks, provided by fMRI
 438 scans.
 439

440 Secondary outcome variables include changes in scores on measures of depression and suicide (DSSI-SS; PHQ-9), anxiety
 441 (GAD-7), sleep impairment (PROMIS; ISS; STOP), general health and functioning (VR-12; BIPF), and alcohol and substance
 442 use (FTND; FTND-ST; AUDIT).
 443
 444
 445
 446

447 **6.4.3 Hypotheses and Specific Data Analysis Plans.**
 448

449 Hypothesis 1: There will be significant overlap between tinnitus distress and PTSD symptoms, as measured by the
 450 Clinician Administered PTSD Scale for DSM-5 (CAPS-5), the PTSD Checklist for DSM-5 (PCL-5), the Tinnitus Functional
 451 Index (TFI), and Tinnitus Acceptance Questionnaire (TAQ). Findings will help clinicians' understanding of the distinct ways
 452 in which each disorder contributes to functional impairment. Results will substantially improve clinicians' ability to
 453 conceptualize patients with comorbid tinnitus and PTSD.
 454

455 Analysis plan: Non-inferential statistics will be calculated to include central tendencies, standard deviations, and
 456 alpha coefficients. Unusual distributions, missing data, or outliers will be identified. PTSD symptom cluster
 457 severity (intrusions, avoidance, negative alterations in mood and cognition, and hyperarousal) will be calculated
 458 using the data gathered from the CAPS-5. Tinnitus domains of distress will be calculated using the data gathered
 459 from the Tinnitus Functional Index. Pearson product-moment correlation coefficient analyses will be used to
 460 examine the overlap between tinnitus and PTSD.

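### The mid-treatment scan cannot support a causal conclusion about CPT in a single-arm trial, and no stated imaging contrast uses it

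*Combined protocol and SAP*

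**What the plan says.** Section 5 sets out the design: "The study will use a one-way experimental design, with one level of intervention", namely CPT. Section 6.1.8 confirms that all participants "will receive treatment with CPT, as it is typically conducted in the VA or another clinic". Scans are taken before treatment, between Sessions 6 and 7, and one month after treatment. Section 6.1.7 pays participants "for each neuroimaging scan: once prior to enrolling in Cognitive Processing" Therapy, once at mid-treatment and once at follow-up, and the table in section 6.2 shows the same three scans.

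Section 6.4.2 makes imaging a primary outcome: "The additional primary outcome is changes in functional activity within resting-state networks, provided by fMRI" scans. Section 6.4.1 says that 10 participants give adequate power to detect network differences "from pre-, mid- and to posttreatment fMRI scans".

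For Aim 3, section 6.4.3 plans an Independent Components Analysis "using analysis of variance (ANOVA) comparing Baseline versus Posttreatment factors", with demographic variables regressed out. The next sentence is "The mid-treatment scan will be used to infer causal effects of Cognitive Processing Therapy by demonstrating the temporal changes in resting-state networks". The missing-data paragraph follows directly and says that, under missing at random, "likelihood-based mixed model analysis will provide valid inferences using data from all cases with any outcome data". The abstract also promises to characterise the two disorders causally by means of causal modelling, but section 6.4.3 specifies no such model.

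**The concern.** There are two linked problems.

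The first is the conclusion. The plan assigns the mid-treatment scan the task of showing that CPT causes network change. A third time point adds detail to a trajectory. It does not supply a comparison with what would have happened without CPT.

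The second is the analysis. The scan meant to carry this conclusion appears in no stated test. Baseline-to-mid, mid-to-follow-up and a trend over three scans would each count as a temporal change, and the plan does not choose among them.

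Followed as written, the plan would report an uncontrolled time course on a primary outcome as an effect of treatment, through a contrast chosen after the fact.

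**Working it through.** **The plan's own figure.** The table in section 6.4.1 adds up: 10 required + 18 screened out + 2 withdrawn = 30; 18/30 = 60% and 2/30 = 6.7%. The 10 itself cannot be reproduced, because no significance level, sidedness, power, effect size or SD is given.

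**What the design identifies.** The observed change between two scans is the sum of any CPT effect and any change that would have occurred anyway. Separating the two needs either a concurrent control or an estimate of the pre-treatment trend. Sections 5 and 6.1.8 rule out the first. A single pre-treatment scan (sections 6.1.7 and 6.2) rules out the second, since one point gives no slope. Adding a mid-treatment scan turns one such sum into two and leaves both unidentified.

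**Where the mid-treatment scan appears.**

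| Place | Scans named |
|---|---|
| 6.4.1, sample size | pre, mid, post |
| 6.4.3, Hypothesis 3 | one month after CPT |
| 6.4.3, ANOVA | baseline, posttreatment |
| 6.4.3, causal sentence | mid-treatment, no model or contrast |

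The sample-size text and the analysis text therefore differ on which scans are compared.

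**Illustration of drift.** The drift sizes and the two-sided 5% level are assumptions. Take a paired t test with n = 10, df = 9, critical t = 2.262 and noncentrality d × √10, where d is non-CPT drift in SDs of within-person change and the CPT effect is zero. For d = 0.5 the noncentrality is 0.5 × 3.162 = 1.58.

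| d | Significant, either direction | Significant in the drift direction |
|---|---|---|
| 0 | 5.0% | 2.5% |
| 0.2 | 8.8% | 8.2% |
| 0.3 | 13.6% | 13.4% |
| 0.5 | 29.3% | 29.3% |
| 0.8 | 61.6% | 61.6% |

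**Does an orderly mid-treatment value help?** I simulated 100,000 trials with n = 10, zero CPT effect, linear drift and independent scan errors. The mean fell in the order baseline > mid > follow-up in 58% of trials for a total drift of 0.5 SD, and in 80% for 0.8 SD. With no drift it was 17%, that is 1 in 6. A mid-treatment value lying between the other two is thus what drift alone tends to produce.

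**Open choice of contrast.** I simulated 400,000 trials with n = 10, normal data and no change at all, testing each contrast at 5%. At least one of the two contrasts that involve the mid-treatment scan was significant in 9% to 10% of trials, and at least one of all three pairwise contrasts in 12% to 13%. The ranges cover equal correlation between scans and an AR(1) correlation of 0.7.

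**Detectable change with 10 complete participants** (80% power, two-sided 5%, before demographic adjustment). With df = 10 − 1 = 9 (paired test or unstructured covariance) it is 0.996 SD of within-person change. With df = (3 − 1) × (10 − 1) = 18 (random intercept) it is 0.94 SD.

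**Why a small-sample correction is needed.** Using 1.96 in place of the t quantile gives a true type I error of 8.2% at df 9 and 6.6% at df 18.

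**The case against.** The strongest reply has four parts.

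- *The drift figures say nothing specific to the mid-treatment scan.* This stands. They apply to any uncontrolled paired test of 10 people, and the documents give no basis for a drift size. A reader might take them as this trial's false-positive rate, but they are not. The defect is read from the text and needs none of them.
- *The plan nowhere says it will run several unadjusted mid-scan tests.* This also stands. The 9% to 13% shows what an unstated contrast leaves open, not what is planned.
- *The missing-data paragraph covers the scans.* It may. A reader might infer that people who stop early are lost from the imaging analysis, because section 9.0 follows them up without fMRI and a two-scan ANOVA needs both scans. The documents do not establish this. The mixed-model paragraph comes directly after the ANOVA and imaging is a primary outcome, so it can be read to retain their scans. The loss arises only if that model is not applied to imaging. Section 6.4.1 also budgets 2 withdrawals on top of the 10 required.
- *Temporal order supports causation, and the abstract names causal modelling.* Order in time is necessary but not sufficient. Every scan after the first follows the start of CPT and also follows the passage of time. The abstract gives no model, and section 6.4.3 supplies no lag or mediation test.

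That this is a small study argues for modest wording. It does not rescue the causal sentence.

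**Conclusion.** The point holds on two counts, with high confidence, and should be fixed. The causal use of the mid-treatment scan is not supported by a single-arm design with one pre-treatment scan. That scan also enters no stated contrast, although the sample size is justified on it.

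Neither conclusion rests on an assumed number. How far non-CPT change would mislead is unknown. Under assumed drifts of 0.2 to 0.8 SD, a significant baseline-to-follow-up change would appear 9% to 62% of the time with no CPT effect.

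Two further inferences are not supported. The documents do not show that early stoppers will be dropped from the imaging analysis. They also give too little to say that 10 participants are too few for the change the sponsor expects, because no expected change is stated.

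**What to change.** 1. **Wording.** Replace the causal sentence in section 6.4.3 with: *Changes in resting-state networks are reported as within-person change over the course of CPT; without a control arm they are not attributed to CPT.* Qualify the abstract's promise of causal characterisation in the same way. In Hypothesis 3 (sections 3 and 6.4.3), let the closing clause say that a decrease would be *consistent with a possible role of cognitive control*.
2. **Analysis.** Use one repeated-measures mixed model for imaging, with scan (baseline, mid-treatment, one-month follow-up) as a three-level within-person factor. Include all available scans, apply a small-sample degrees-of-freedom correction such as Kenward-Roger, and keep the demographic adjustment already planned. State that this is the likelihood-based model of the missing-data paragraph. The contrast for Hypothesis 3 is baseline-to-follow-up attention-limbic connectivity. The within-network measures of section 6.4.2 use the same model and remain reported outcomes, so the primary imaging outcome is not narrowed. Contrasts involving the mid-treatment scan are time-course estimates with 95% confidence intervals. Named contrasts with a multiplicity rule would be a defensible alternative.
3. **Sample size.** Make the sentence in section 6.4.1 refer to the baseline-to-follow-up contrast. If a detectable change is quoted, label it approximate: about 0.94 to 1.0 SD of within-person change for 10 complete participants, 80% power, two-sided 5%, depending on the error degrees of freedom and before demographic adjustment.

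The cost is text and slightly more analysis, with no new participants, scans or arm. The trial would describe change during CPT without attributing it to CPT, and the model relies on missing at random for people without a follow-up scan.
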